### 3.4.3. Additional Exclusion Criteria Clarification for SBP/DBP and QTcF

Subjects presenting with a history of hypertension that is uncontrolled during screening (i.e., SBP > 140 mmHg and/or DBP > 90 mmHg), whether on treatment or not, will be excluded. Subjects who had high or uncontrolled BPs in the past and are currently controlled with given therapies would be eligible for this study.

Independent of past history, if a subject has a sustained resting SBP/DBP > 140/90 mmHg at Visit 1 (V1) or V2, those subjects should be excluded. If a subject has a

sustained SBP/DBP  $> 140/90$  mmHg at a visit after V2, those subjects should be discontinued from the study. Any subject without a known history of hypertension that presents at screening with SBP/DBP  $> 140/90$  mmHg should be excluded (if at V1 or V2) or discontinued (if at a visit after V2) if the BP reading is due to suspected hypertension or another pathological condition, not if due to a transient fluctuation, based on the Investigator's evaluation. If the Investigator believes the BP is falsely elevated, they should repeat the assessment 2 to 3 times with the subject in a semi-reclined position in a quiet room. Subjects with persistent elevations, despite repeat assessments, should be excluded and referred to an appropriate healthcare provider for further assessment.

For subjects presenting at screening with an ECG QTcF  $> 450$  msec (based on central ECG interpretation), the following procedures should be conducted:

1. Wait until all other inclusion and exclusion criteria have been satisfied.
2. If the subject otherwise appears eligible for the study, with prior Medical Monitor approval, have the subject return and conduct 2 ECGs with a minimum of 5 minutes between tracings.
3. Transmit these additional ECGs to ERT for central interpretation.
4. Based on the central reader interpretation, if both repeat ECGs show a QTcF  $\leq 450$  msec, the subject may continue in the study at the Investigator's discretion. If one or both repeat ECGs show QTcF  $> 450$  msec, the subject must be screen failed based on exclusion criteria #20.

At Visit 2 or Visit 3, additional clarification for QTcF  $> 450$  msec (based on ERT interpretation) is as follows:

1. For QTcF between 451 msec and 460 msec (inclusive), the subject may continue in the study if the Investigator assesses the ECG as not clinically significant (NCS).
2. For QTcF  $> 460$  msec:
  - a) Instruct the subject not to take the study drug until further notice.
  - b) If the Investigator has assessed the ECG as NCS, have the subject return, after Medical Monitor approval, to conduct 2 ECGs with a minimum of 5 minutes between tracings.
  - c) Transmit these additional ECGs to ERT for central interpretation.
  - d) If one or both ECGs again shows QTcF  $> 460$  msec, based on the central reader, then the subject must be discontinued from the study.

### 3.5. DETERMINATION OF SAMPLE SIZE

Approximately 600 subjects will be randomized for the DB1 treatment period. Subjects who discontinue participation without completing the study protocol will not be replaced.

The first co-primary endpoint is the comparison of the proportion of subjects who are pain-free at 2 hours after the first dose of study drug. It is assumed that 17.6% of

placebo and 29.2% of DFN-15 (treated) subjects will be pain-free at 2 hours. A sample size of 600 subjects will provide 88% power to detect this assumed difference between placebo and DFN-15 at a 5% (2-sided) level of significance and with a 15% dropout rate.

The second co-primary endpoint is the comparison of the proportion of subjects who are free from their Screening MBS among nausea, photophobia, and phonophobia at 2 hours after the first dose of study drug. It is assumed that 28.2% of placebo and 44.7% of DFN-15 (treated) subjects will be free from their Screening MBS at 2 hours. A sample size of 480 subjects will provide 94% power to detect this assumed difference between placebo and DFN-15 at a 5% (2-sided) level of significance and with a 15% dropout rate.

Since the sample size for the first co-primary endpoint is larger than that of the second co-primary endpoint, the larger sample size will be used for the study.

### **3.6. TREATMENT ASSIGNMENT & BLINDING**

The DFN-15-CD-006 study is a randomized, 2 DB treatment period, placebo-controlled study. Eligible subjects will be randomized in a 1:1 ratio in both DB periods to receive orally either DFN-15 or matching placebo, to be used in one migraine attack. The randomization schemes for both DB periods will be generated by the biostatistics group of [REDACTED]. The interactive web response system (IWRS) will assign the appropriate study kit to each subject for each DB treatment period. If a subject discontinues from the study after randomization, the subject identification (ID) number and randomization number will not be reused, and the subject will not be allowed to re-enter the study.

All randomization data will be kept strictly confidential and accessible only to authorized personnel until the time of unblinding after database lock at the end of the study. Blinding is critical to the integrity of this clinical study; however, in the event of a medical emergency for an individual subject, in which knowledge of the treatment assignment is critical to the subject's management, the blind for the subject may be broken by the Investigator (or designee) by contacting IWRS. Before unblinding, the Investigator (or designee) should have determined that the treatment information is necessary to decide the subject's immediate management, and must make every effort to contact the Medical Monitor prior to unblinding. In many cases, especially if the emergency is clearly not related to study treatment, the problem may be properly managed without unblinding by assuming that the subject is receiving active treatment. In cases of accidental unblinding or when the Medical Monitor cannot be contacted prior to unblinding, the Medical Monitor should be contacted as soon as possible after the breaking of the blind and every attempt to preserve the blind for all other study staff should be made.

### **3.7. ADMINISTRATION OF STUDY DRUG**

During the DB1 treatment period, randomized subjects will be instructed to use the study drug [either DFN-15 120 mg (25 mg/mL) or a matching placebo] in 1 migraine attack as soon as (and no more than within 1 hour after) experiencing moderate to

severe pain (defined as headache pain rating of Grade 2 [moderate] or Grade 3 [severe] on pain severity scale of 0 to 3). In the DB2 treatment period, eligible re-randomized subjects will receive study drug to treat 1 migraine attack at any pain level.

Study drug should only be used to treat a new migraine attack, not a recurrence, and there should be at least 48 hours of pain and symptom freedom from a previous attack.

At the end of DB1 treatment period and prior to the start of the DB2 treatment period, all used and unused study drug will need to be returned. At the end of the study, subjects will be required to return all used and unused study drug, study drug containers, and a completed eDiary.

### **3.8. STUDY PROCEDURES AND FLOWCHART**

The duration of study participation will be up to approximately 13 weeks, including a screening period of approximately 3 weeks, 2 DB treatment periods with up to 4 weeks allowed to experience and treat a migraine attack in each, and 2 to 7 days for subjects to return to the site after treatment.

[Table 1](#) summarizes the planned study assessments.

[Table 2](#) summarizes the eDiary assessments.

Table 1 Schedule of Assessments

	V1	V2	V3	V4  /ET 
	Screening	Randomization	End of DB1 period Re-randomization	End of DB2 period (end of study) or ET
Assessment	Approximately 21 days 	Baseline-Day 0  Study drug dispensed should be used to treat a migraine attack as soon as (and no more than within 1 hour after) experiencing moderate or severe pain.  Treatment should be completed within 4 weeks from Baseline.	Visit is expected within 2-7 days of treating a migraine attack with study drug dispensed at V2.  Study drug dispensed at this visit should be used within 4 weeks to treat a migraine attack at any pain level.	Visit is expected within 2-7 days of treating a migraine attack with the study drug dispensed at V3.  Once randomized, the total duration of each subject's participation in the study would be up to 10 weeks from Baseline.
Informed consent	X			
Inclusion/Exclusion criteria	X	X	X	
Subject eDiary instructions and dispensation 	X	X	X	
Adverse events (AEs) review	X	X	X	X
Demographics	X			
Medical history and prior medications	X	X		
Migraine history (including MBS for the co primary analysis) and current treatment status	X			
Physical examination and suicidality check 	X	X	X	X
Height and weight	X			X 

## Statistical Analysis Plan

[name], Ltd.  
Protocol #DFN-15-CD-006

Amendment V3.0

Vital signs (sitting SBP/DBP, pulse rate, body temperature)	X	X	X	X
Serum pregnancy test (hCG) 	X			
Urine pregnancy test 		X	X	X
Clinical laboratory tests (hematology, chemistry, urinalysis); TSH at Screening	X	X	X	X
Glycosylated hemoglobin (HbA1c)	X			X
Serology (HIV, HBsAg, HCV)	X			
Urine drug test and ethanol screen	X	X	X	X
12 lead ECG	X	X	X	X
Concomitant medication review			X	X
Randomization (V2)/Re randomization (V3)		X	X	
Dispense DB study drug 		X	X	
Subject study drug compliance and accountability 			X	X
Subjects record data in the eDiary 				→
Review, confirm, and ensure proper recording of the subject eDiary entries 		X	X	X
Collect eDiary 				X

Abbreviations: AE adverse event; DB double blind; DBP diastolic blood pressure; ECG electrocardiogram; eDiary electronic diary; ET early termination; HbA1c glycosylated hemoglobin; HBsAg hepatitis B surface antigen; hCG human chorionic gonadotropin; HCV hepatitis C virus; HIV human immunodeficiency virus; SBP systolic blood pressure; TSH thyroid stimulating hormone; V Visit

**Statistical Analysis Plan**

**[name], Ltd.**  
**Protocol #DFN-15-CD-006**

**Amendment V3.0**

 V4 will occur up to 10 weeks after baseline (V2).

 Subjects who do not complete both DB periods will complete an ET visit.

 Subjects may be randomized earlier during this period if they meet inclusion/exclusion criteria and headache assessment criteria. The screening period may also be extended based on Investigator judgment and in consultation with the Medical Monitor.

 Before eDiary dispensing, initial screening should determine to the extent possible that the subject may be eligible for the study and is able, willing, and understands after being instructed how to use the eDiary; eDiary will be dispensed once if the subject is randomized and used throughout the DB periods. At V2, randomized subjects will be re instructed and re trained on the eDiary usage to ensure real time entry of predose and postdose assessments and the level of migraine pain to treat (moderate or severe for first treatment and of any pain level for the second). Thereafter, randomized subjects will be re instructed on eDiary usage, and re trained on instructions as needed.

 Physical examination data will be recorded in the source at screening (V1). A complete physical examination will be performed, including examination of head, eyes, ears, nose, and throat [HEENT], heart, lungs, abdomen, skin, cervical and axillary lymph nodes, neurological, and musculoskeletal systems. At other visits, symptom driven limited physical examination will be performed. Any subsequent untoward change during the study will be recorded as an AE. Suicidality risk will be determined and recorded at screening (V1) and checked at all subsequent visits. Significant suicide risk, in the opinion of the Investigator, is exclusionary at V1 and V2. A randomized subject will be discontinued if a significant suicide risk is determined at subsequent visits. At any visit, subjects who are a suicide risk should be referred to a mental health specialist. The Medical Monitor should also be notified.

 Weight only.

 Serum pregnancy test will be performed at screening (V1) for all female subjects of childbearing potential.

 Urine pregnancy tests will be performed at all study visits after screening for all female subjects of childbearing potential.

 Subjects will be instructed by the study site staff on the proper administration of study drug to ensure compliance. Written instructions for use of the study drug will be distributed to Investigator sites, and subjects should be confirmed to have, or be provided with, the instructions every time study drug is dispensed.

 Unused study drug returned by subjects should not be redispensed.

 When the subject experiences a migraine episode, they should contact the site within 1 day of treating with study drug to schedule their next visit. The eDiary will be used to record all migraine attacks treated with study drug during the study period.

 Screening eDiary information will be kept in the source. It is compulsory for all the subjects to check in the eDiary every day during the entire study period. If a subject does not consistently check in or does not report a migraine attack in the eDiary for 2-3 weeks, it is recommended they should be contacted by study staff to check if the subject has technical difficulties or confirm they have not experienced a migraine.

 Arrangements should be made by the site for a timely return of the eDiary device for subjects who screen fail.

**Statistical Analysis Plan****[name], Ltd.**  
**Protocol #DFN-15-CD-006****Amendment V3.0****Table 2 eDiary Assessments**

Assessment/Time	Baseline	DB1 and DB2 Treatment Period					
		Predose	Postdose				
			15, 30, 45 min	1 h and 1.5 h	2 h and 4 h	24 h	
Migraine date/time and aura information, study drug, last food intake and fat content, and rescue medication taken for migraine attacks			As applicable 				
Time to meaningful pain relief (based on subject's perception)			As applicable up to 2 h postdose				
Time to pain freedom			As applicable up to 2 h postdose				
Pain level		X	X	X	X	X	
Functional disability		X			X	X	
Presence of nausea/photophobia/phonophobia and cutaneous allodynia		X	X	X	X	X	
Most bothersome symptom (selected between nausea, photophobia and phonophobia) 		X					
PPMQ R	X					X	
Subject treatment satisfaction					X 		

Abbreviations: h hour(s); min minutes; PPMQ R Patient Perception of Migraine Questionnaire Revised

 End of migraine pain may occur more than 24 hours postdose. The most bothersome symptom will be collected only if more than 1 symptom is present predose; if only 1 symptom is present, it will be considered the most bothersome. Treatment satisfaction baseline for the migraine medication to be collected prior to randomization in the PPMQ R.

## 4. ENDPOINTS

### 4.1. CO-PRIMARY ENDPOINTS

The co-primary endpoints of this study are:

- The proportion of subjects who are pain-free 2 hours postdose compared between DFN-15 and placebo in the DB1 treatment period (defined as a reduction from predose moderate [Grade 2] or severe [Grade 3] pain to none [Grade 0]).
- The proportion of subjects who are free from their Screening MBS among nausea, photophobia, and phonophobia (and have this symptom predose) at 2 hours postdose compared between DFN-15 and placebo in the DB1 period.

### 4.2. SECONDARY ENDPOINTS

Secondary endpoints for each DB period are:

- The proportion of subjects with treatment-emergent adverse events (TEAEs) after study drug compared between DFN-15 and placebo.
- The proportion of subjects who are free from nausea, photophobia, and phonophobia at 15, 30, and 45 minutes and 1, 1.5, 2, 4, and 24 hours postdose compared between DFN-15 and placebo.
- Time to meaningful pain relief (defined as based on subject's perception) within 2 hours postdose compared between DFN-15 and placebo in each treated attack.
- Time to pain freedom within 2 hours postdose compared between DFN-15 and placebo.
- The proportion of subjects who have pain relief at 15, 30, and 45 minutes and 1, 1.5, 2, 4, and 24 hours postdose compared between DFN-15 and placebo. Headache pain relief is defined for DB1 as a reduction from moderate or severe pain prior to dosing to mild or none postdose, and for DB2 as moderate or severe pain predose reduced to mild or none postdose, or mild pain predose reduced to none postdose.
- The proportion of subjects who are pain-free at 15, 30, and 45 minutes and 1, 1.5, 2 (DB2 period), 4, and 24 hours postdose compared between DFN-15 and placebo.
- The proportion of subjects with their Screening MBS (and have this symptom predose) absent at 15, 30, and 45 minutes, and 1, 1.5, 2 (DB2 period), 4, and 24 hours postdose compared between DFN-15 and placebo.
- Change in functional disability score at 2, 4, and 24 hours postdose compared between DFN-15 and placebo.
- Among those reporting cutaneous allodynia predose, the proportion of subjects who are pain-free at 2 and 4 hours postdose compared between DFN-15 and placebo.

- The proportion of subjects who are pain-free at 2 and 4 hours postdose whose BMI is < 30 vs. subjects whose BMI is  $\geq$  30, and whose BMI is < 25 vs. subjects whose BMI is  $\geq$  25.
- The proportion of subjects who have pain recurrence between 2 to 24 hours (i.e., pain-free at 2 hours postdose, with pain [mild, moderate, or severe] reported at 24 hours postdose) compared between DFN-15 and placebo.
- The proportion of subjects who have sustained pain relief at 2 to 24 hours postdose (i.e., pain relief at 2 hours postdose, with no use of rescue medication and no worsening of headache pain within 2 to 24 hours postdose) compared between DFN-15 and placebo.
- The proportion of subjects who have sustained pain freedom at 2 to 24 hours postdose (i.e., pain-free at 2 hours postdose, with no use of rescue medication, and no recurrence of headache pain within 2 to 24 hours postdose) compared between DFN-15 and placebo.
- The proportion of subjects who use rescue medication after 2 hours (2 to 24 hours) postdose compared between DFN-15 and placebo.
- Treatment satisfaction at 2 hours and 4 hours postdose as determined on a 7-point scale compared between DFN-15 and placebo. DFN-15 will also be compared to same question in the Baseline PPMQ-R.
- Treatment satisfaction as measured by PPMQ-R at 24 hours postdose compared between DFN-15 and placebo.

## 5. ANALYSIS SETS

### 5.1. SCREENED SET

The Screened Set will include all screened subjects. The set of analyses including subject listings and summary tables of subject disposition will be analyzed based on all eligible screened subjects who are databased for the study.

### 5.2. RANDOMIZED SET

Each DB treatment period will have a Randomized Set. The randomized set for DB1 will include all subjects who give informed consent and are eligible for and randomized into the DB1 treatment period. The randomized set for DB2 will include all subjects in the randomized set for DB1 who are eligible for and are re-randomized into the DB2 treatment period.

### 5.3. SAFETY SET

The Safety Set (SS) will include all subjects who took at least one dose of DB study drug during one or both treatment periods, and have it recorded in their eDiary. Subjects will be analyzed according to the treatment they receive. The Safety Set 1 (SS1) will include randomized subjects who took at least one dose of DB study drug during the DB1 treatment period. The Safety Set 2 (SS2) will include subjects who were re-randomized and took at least one dose of DB study drug during the DB2 treatment period. The SS, SS1, and SS2 will be used for all analyses of safety endpoints including summaries of TEAEs, ECGs, and clinical laboratory results.

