### **8.6 Treatment Compliance**

Subjects will be instructed by the study site staff on the proper administration of study drug to ensure compliance. Written instructions for use of study drug will be distributed to the Investigator sites, and subjects should be confirmed to have, or be provided with, the instructions every time study drug is dispensed.

See [Section 5.1](#) and [Section 8.5.2](#) for details on timing of dosing with study drug and use of rescue medication.

At the end of the DB1 period (V3), subjects will be required to return all used and unused study drug from DB1 period before any study drug for the DB2 period will be dispensed.

At V4/ET, subjects will be required to return all used and unused study drug, study drug containers, and completed eDiary.

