### ***Safety Population***

The safety population will include all subjects who receive at least one dose of DB study drug during one or both treatment periods and have it recorded in their eDiary. Each DB treatment period will have a safety population which will include all subjects who were randomized in the DB treatment period and who received at least one dose of DB study drug during the treatment period.

Additional information is included in the SAP. The SAP will serve as a compliment to the protocol and supersedes it in case of differences.

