## 7.5. MEDICATION

### 7.5.1. Study Drug Accountability

All data in the study drug accountability log will be listed, which will include the dates and kit number(s) of the drug dispensed and returned.

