### **9.3. ADVERSE EVENTS**

All AEs will be coded using the Medical Dictionary for Regulatory Activities (MedDRA; version 19.0 or higher). Migraine headaches will not be captured as AEs. Migraine headaches will be captured by the subject in the eDiary provided to them, and the information will be entered into the appropriate eCRF page.

All AEs will be listed by subject. The following listings of AEs will be provided:

- All AEs
- Study-drug related AEs
- Serious adverse events (SAEs)
- AEs leading to death
- Adverse events leading to study-drug termination

Only TEAEs will be included in summary tables. Summaries for AEs will be presented for the SS, SS1, and SS2. An overall summary table of TEAEs will be produced for the following categories:

- Any TEAE
- Study-drug related TEAEs
- Serious TEAEs
- TEAEs leading to study-drug termination
- TEAEs leading to death

All TEAEs will be classified by system organ class (SOC) and preferred term (PT). Frequency count and the number of unique subjects of a TEAE will be tabulated by treatment(s) received. For the number of unique subjects reporting, if a subject reported more than one AE that was coded to the same SOC or PT, the subject will be counted only once for that specific SOC or PT.

The following summaries of TEAEs will also be provided:

- TEAEs by SOC and PT
- Study-drug related TEAEs by SOC and PT
- Serious TEAEs by SOC and PT
- TEAEs by maximum severity (mild, moderate, severe or missing) by SOC and PT
- TEAEs by strongest causality relationship (not related, possibly related, probably related, definitely related or missing) by SOC and PT

For TEAEs presented by relationship to study treatment(s), the strongest relationship to study treatment(s) during the study will be presented for each subject if coded to the same SOC or PT. For TEAEs presented by severity, the worst severity during the study will be presented for each subject if coded to the same SOC or PT. TEAEs with missing causality will be counted as related. TEAEs with missing severity will be counted as severe. The same will be true in the individual summaries.

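### The overall Safety Set requires an eDiary record of the dose but its two period sets do not, so the pooled safety tables can omit subjects who were dosed

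*SAP*

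**What the plan says.** SAP 5.3 defines three safety sets in one paragraph.

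- **SS (overall):** subjects who "took at least one dose of DB study drug during one or both treatment periods, and have it recorded in their eDiary".
- **SS1:** "The Safety Set 1 (SS1) will include randomized subjects who took at least one dose of DB study drug during the DB1 treatment period".
- **SS2:** subjects who were "re-randomized and took at least one dose of DB study drug during the DB2 treatment period".

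Only SS carries the diary condition. SAP 11 repeats the paragraph as a change from the protocol. Protocol 10.2 is built the same way: the overall population must "receive at least one dose of DB study drug during one or both treatment periods and have it recorded in their eDiary", while each period's population is made up of subjects "who were randomized in the DB treatment period and who received at least one dose of DB study drug during the treatment period".

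SAP 9.3 states: "Summaries for AEs will be presented for the SS, SS1, and SS2". SAP 9.4 to 9.6 use the same three sets for laboratory data, vital signs and ECGs. SAP 7.4 (medical history) and SAP 7.5.2 (prior and concomitant medication) use SS only.

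The trial also collects evidence of dosing outside the diary. Protocol 8.6 states: "At the end of the DB1 period (V3), subjects will be required to return all used and unused study drug from DB1 period". It asks for the same, with the containers, at the final visit. SAP 7.5.1 states: "All data in the study drug accountability log will be listed".

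**The concern.** A safety set should follow exposure. Here the pooled set follows exposure plus a diary entry, and nothing in either document adds back a subject whose dose is known only from a returned bottle or a report to the site.

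Two things are at stake. First, the pooled set can be smaller than the two sets it should combine, so counts in the disposition table (SAP 7.1) and the safety tables may not reconcile. Second, the pooled AE percentages can lose exposed subjects from numerator and denominator.

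The protocol itself expects diary failures. Section 9.1.1 provides for subjects who do not check in or have technical difficulties, and section 9.2.1.2 allows predose assessments to be entered afterwards. SAP 9.2 already accepts rescue medication reported outside the eDiary, so refusing such evidence for study drug is inconsistent.

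**Working it through.** **Step 1: apply the rules as written.** The plan states no figure to reproduce; the check is one of set membership. The inputs are the three definitions in SAP 5.3. DB2 dosing is taken to follow DB1 dosing, and one recorded dose is taken to satisfy the SS condition, which is the plain reading.

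| Dosed DB1 | Dosed DB2 | Recorded DB1 | Recorded DB2 | SS | SS1 | SS2 |
|---|---|---|---|---|---|---|
| yes | no | yes | – | in | in | out |
| yes | no | **no** | – | **out** | in | out |
| yes | yes | yes | yes | in | in | in |
| yes | yes | yes | no | in | in | in |
| yes | yes | no | yes | in | in | in |
| yes | yes | **no** | **no** | **out** | in | in |

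In two of the six dosed patterns the subject is in a period set but not in SS. SS is therefore not the union of SS1 and SS2.

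**Step 2: trace the effect through the outputs.** For a subject in either of those two rows:

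- Pooled AE, laboratory, vital-sign and ECG tables: missing.
- Medical history and prior/concomitant medication tables (SS only): missing.
- By-period AE, laboratory, vital-sign and ECG tables (SS1, SS2): present, as worded.
- AE listings, which cover all AEs by subject (SAP 9.3): present.

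**Step 3: illustrate the size.** The documents give neither an AE rate nor a rate of unrecorded dosing, so these inputs are assumptions. The number dosed per arm uses the planned 600, the 15% dropout in protocol 10.7 and 1:1 allocation: 600 × 0.85 / 2 = 255. This treats every dropout as undosed.

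If 1% to 5% of the 510 dosed subjects had no recorded dose, that would be 510 × 0.01 = 5.1 to 510 × 0.05 = 25.5, or about 5 to 26 subjects over both arms. If the percentage is applied to DB1 doses, this is an upper bound, because a subject whose DB2 dose was recorded returns to SS.

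Let x subjects in an arm have an AE, and let m have no recorded dose. The true rate is x/255. The SS rate is (x − m)/(255 − m) if all m had an AE, and x/(255 − m) if none did.

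For x = 26 (true rate 26/255 = 10.2%):

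| m | all m had an AE | none of m had an AE |
|---|---|---|
| 1 | 25/254 = 9.8% | 26/254 = 10.2% |
| 3 | 23/252 = 9.1% | 26/252 = 10.3% |
| 5 | 21/250 = 8.4% | 26/250 = 10.4% |
| 10 | 16/245 = 6.5% | 26/245 = 10.6% |

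If all m had an AE, a true rate of 13/255 = 5.1% would read 4.7%, 4.0%, 3.2% and 1.2% for m = 1, 3, 5 and 10. A true rate of 51/255 = 20.0% would read 19.7%, 19.0%, 18.4% and 16.7%.

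For a single rare event, the pooled table could read 0/254 instead of 1/255 (0.4%), while the period table and the listing showed the case.

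**The case against.** The strongest objection is that the exclusion will rarely apply and does not hide anyone. SS needs only the dose entry, not the postdose entries. Protocol 9.2.1.4.1 has the subject log the dose date and time in real time. Someone who becomes unwell afterwards would lose later entries, which bears on the full analysis sets rather than SS. Sites review the diary and drug accountability at Visits 3 and 4, inconsistent data are queried (protocol 11.1.3), and a blinded review precedes unblinding (protocol 10.1). This all stands, and it makes large numbers unlikely. It does not change the membership rule: a query may detect an unrecorded dose, but the definition still keeps that subject out of SS.

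Three stronger readings are tempting, and the documents support none of them.

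- **That the rule selectively removes subjects with early adverse events.** A reader might point to the 0.67 h time to peak in protocol 8.2. That section is describing test doses of the 50 mg/mL solution, whereas the trial product is 25 mg/mL. An event at about that time would also come after the dose entry was due.
- **That these subjects vanish from safety reporting.** As worded, SS1, SS2 and the listings keep them, and SAEs are reported through the investigator (protocol 9.2.2.7). The SAP does not name the source of dosing for SS1 and SS2. If programmers used the diary there too, the loss would be wider but the mismatch with SS would disappear. Both problems cannot be claimed at once.
- **That the accountability log supplies the missing dose date.** SAP 7.5.1 describes dates and kit numbers dispensed and returned, not the date of dosing. A used bottle also does not prove that the contents were swallowed.

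**Conclusion.** The inconsistency is real and follows from the text alone. A subject with no recorded dose belongs to one or both period sets but not to the overall set. The consequence is limited to the pooled safety tables and the SS-only background tables. The number affected is unknown and probably small, and the percentages above rest wholly on assumed AE and non-recording rates. The direction of any bias is also unknown: the pooled rate falls if the omitted subjects had AEs and rises slightly if they did not. This should be fixed before database lock, but it does not touch the co-primary analyses and is not a critical defect.

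**What to change.** In SAP 5.3, with SAP 11 and protocol 10.2 aligned:

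1. Delete the clause requiring an eDiary record, and define SS as the union of SS1 and SS2.
2. Name the accepted evidence of dosing for all three sets: an eDiary entry, a returned used bottle with site confirmation, or an AE/SAE report that establishes dosing.
3. Add a dose-date rule for doses without a diary time, because the treatment-emergent window in SAP 6.2.5 and the date imputation in SAP 6.3 both depend on the dose date. Take the date from a site query or source record. Failing that, use a conservative rule bounded by the dispensing and return dates, so that AEs starting in that interval count as treatment-emergent.
4. List the subjects whose dosing is known only from outside the eDiary.
5. Reconcile returned drug, diary and AE records before database lock, so that set membership is settled before unblinding.

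The SAP takes precedence where the two documents differ (protocol 10.1), so the SAP change is the essential one. The cost is a short text change, one date rule and a pre-lock reconciliation of data already collected. The downside is that a few dose dates will be approximate.
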